3.1 Confidence Intervals and *p*-Values

We will report statistical significance as determined in statistical null hypothesis tests by means of p-values. A level of significance of 0.05 will be used throughout the analyses. Accordingly, we will report two-sided 95% confidence intervals of coefficient estimates.

We will use a mixed-effects regression model for assessment of the primary objective and we will base rejection of the null hypothesis (no difference in effect on HPVv counts at T6 between the control and

intervention group related to the study hypothesis (see section 1.2) on statistical significance of a specific fixed effect coefficient estimate (see section 4.2.3).

Secondary outcomes will be assessed in an exploratory manner, and no adjustment for multiplicity will be implemented. We will judge resulting *p*-values with appropriate caution and consider the corresponding effect sizes.

3.2 Analysis Populations

For each of the primary and secondary objectives, we will define an intention-to-treat analysis (ITT) population as the population of all GPs who underwent randomization, regardless of participation in the educational session at Ti and loss to follow-up.

For each of the primary and secondary objectives, a per-protocol analysis (PPA) population will include all GPs who participated in the educational session at Ti.

Handling of missing data in the ITT and PPA populations is described in section 4.3.

3.3 Variables and Measurements

This section describes the variables assessed during the study. The corresponding timings are described in section 2.8 and summarized in Table 1.

3.3.1 Baseline Data

GPs will be asked to provide the total number of vaccination doses administered during Pb for each of the vaccinations that will also be reported during the study and follow-up periods. GPs will be provided the choice among Never; Rarely (1–5 doses); Occasionally (6–10 doses); Regularly (at least 11 doses). For Pb, no information will be collected on demographic data of patients who obtained the vaccination or on whether the vaccinations were administered as first/second/third doses or booster vaccinations.

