1.2 Hypotheses

The primary study hypothesis is that a multifaceted, targeted intervention with a focus on teaching a presumptive announcement recommendation style will result in an increase of HPVv rates of patients aged 18 years and older in Swiss primary care. The analyses presented in this document will assess the efficacy of such an educational intervention aimed at GPs will be included in the final study report.

2 Study Methods

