2.1 Trial Design

2.1.1 Study Population

The study population will consist of GPs working in practices in German-speaking Switzerland. Fulfilment of all inclusion-exclusion criteria will be reviewed by the investigator or qualified designee to ensure that subjects qualify for the study.

Inclusion criteria:

- i) The GP works in the primary care setting.
- ii) The GP has been providing vaccinations according to the Swiss ministry of health (recommended basic and recommended additional vaccinations) for at least six months in their practice before study start. In detail: combined measles, mumps and rubella (MMR), meningococci, pneumococci, HPV, tick-borne encephalitis (TBE), chickenpox, shingles, and hepatitis A/B (combination and single vaccinations).

Exception: GPs not registered in the cantonal HPVv program can be included if they are willing to join the programme and have the eligible patient population in their practice to administer vaccinations.

Note: 'Providing vaccinations' means that a GP (or the practice they work at) in principle offers the vaccination to the patients. There is no need for a minimum number of vaccinated patients in the last six

months before inclusion into the study. For example, GPs registered in the cantonal HPVv program can be included even if they have not administered any HPVv doses during the previous six months.

Exclusion criteria:

- The GP predominantly provides pediatric care (reported by the GP as >50% of consultations).
- The GP predominantly provides gynecological care (reported by the GP as >50% of consultations).
- The GP is a school physician or provides vaccinations on behalf of schools.

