2.2 Randomization

Randomization will occur cluster-wise on level of the practices where the enrolled GPs work. A statistician external to the study group will carry out stratified randomization into the active or control intervention group using the Shiny Balancer tool, which facilitates balanced allocation in cluster-randomised trials (1).

Stratification will occur according to the following factors:

- Participation status in the cantonal HPVv program at inclusion (yes/no).
- Estimated number of HPVv administered during the baseline period (4 categories, see section 3.3.1).

GPs enrolling in the trial when randomization of their practice has already taken place will be allocated to the corresponding study arm. GPs will need to be registered in the cantonal HPVv program before initiation of outcome measurements.

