3.3.2 Outcome Measurements

GPs will document all vaccines administered to patients aged at least 18 years starting on T0 and ending on T12. We will provide enrolled GPs with separate standardized case report forms (CRFs) to report all vaccinations administered during the study period and the follow-up period, respectively. GPs will report the following vaccinations: HPV, MMR, meningococci, pneumococci, TBE, chickenpox, shingles, and hepatitis A/B (combination and individual vaccines). The GPs will send CRFs to the Institute of Primary Care every two months by mail. For the study period and the follow-up period, GPs will report age and sex of patients to whom these vaccines are administered. In addition, only during the study period, they will report whether vaccinations are administered as first/second/third doses or as booster vaccinations as well as whether they are administered upon request by the patient or as recommended by the GP. During the follow-up period, they will only indicate whether vaccinations are administered as first or later doses (without further specification).

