4.1.2 Secondary Objectives

- (1) To compare the first-dose HPVv counts at T3 and T12 between the intervention group and the control group.
- (2) To compare the number of overall HPVv counts at T3, T6, and T12 between the intervention group and the control group.
- (3) To compare the change of overall HPVv counts at T3, T6 and T12 with respect to Pb between the intervention group and the control group.
- (4) To compare the change in HPV-related knowledge at T6 with respect to Ti (before delivery of the intervention) between the active intervention group and the control group.
- (5) To compare the change in attitudes towards HPVv at T6 with respect to Ti (before delivery of the intervention) between the active intervention group and the control group.
- (6) To describe demographic characteristics of patients obtaining HPVv (gender and age).
- (7) To describe the following characteristics of administered HPVv: first dose or later vaccination, request of patient or recommendation by GP (or both), and HPVv administered alone or in combination with other vaccines.

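### The baseline HPVv item has no age limit while all vaccination-count outcomes are adults-only, which chiefly weakens secondary objective 3

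*SAP*

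**What the plan says.** **Baseline.** SAP 3.3.1: "GPs will be asked to provide the total number of vaccination doses administered during Pb". The answer is categorical: "GPs will be provided the choice among Never; Rarely (1–5 doses); Occasionally (6–10 doses); Regularly (at least 11 doses". No age limit is attached, and "For Pb, no information will be collected on demographic data of patients who obtained the vaccination".

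**Outcome counts.** SAP 3.3.2: "GPs will document all vaccines administered to patients aged at least 18 years starting on T0 and ending on T12". The hypothesis in 1.2 has the same limit and concerns an "increase of HPVv rates of patients aged 18 years and older in Swiss primary care".

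**Who can enrol.** Section 2.1.1 excludes a GP on this ground: "The GP predominantly provides pediatric care (reported by the GP as >50% of consultations". It also excludes gynaecological practice on the same 50% rule, as well as school physicians and GPs who vaccinate on behalf of schools. A GP with up to half paediatric consultations remains eligible.

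**Uses of the baseline category.**
- Stratification factor (2.2): "Estimated number of HPVv administered during the baseline period (4 categories, see section 3.3.1".
- Candidate covariate in the primary model (4.2.3), one of seven besides study arm, kept only if its univariate p-value is at most 0.2.
- The subgroup variable (4.2.6).
- The reference in secondary objective 3 (4.1.2): "To compare the change of overall HPVv counts at T3, T6 and T12 with respect to Pb". Section 4.2.4 turns this into a yes/no indicator of whether the overall count at T6 exceeds the Pb value.

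**The concern.** The SAP states the adult limit for the outcome counts but not for the baseline item. Section 3.3.1 ties the baseline to follow-up by vaccine, not by patient age. If GPs answer the question as worded, the Pb category can include doses to minors. Because no patient demographics are held for Pb, the analyst cannot restrict it afterwards.

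The consequence is most direct in objective 3. Take a GP who gave 12 HPV doses to minors and none to adults in Pb. This GP is recorded as *Regularly*. The same pattern after T0 gives an adult count of 0. If this GP then starts vaccinating adults, the indicator still shows no increase until the adult count passes the inflated reference.

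The sponsor evidently cares about this kind of matching: section 7 explains the T3 measurement by the wish to be comparable with the baseline period. The window was aligned at T3, while the age range was left open.

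**Working it through.** **No figure in the plan to reproduce.** The SAP gives no expected baseline count and no share of doses to minors. The sample size in 2.4 does not use the baseline category, so it is unaffected.

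**Definitions side by side**

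| | Pb value (3.3.1) | Count used in objective 3 (3.3.2, 4.2.4) |
|---|---|---|
| Age | not limited | 18 or older |
| Window | 3 months | T0 to T6, 6 months |
| Scale | 4 categories | count |

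Two rows bear on the direction of error. Minors in Pb raise the reference and hide increases. The longer window raises the count and creates increases. The window mismatch is certain from the text; the age mismatch follows from the wording of the item.

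**Size, by simulation.** All rates are assumed, with 400,000 GPs per setting and Poisson counts. A GP is flagged as increased when the later adult count falls in a higher category than the Pb value. The SAP does not say how a count is compared with a category, so this rule is also an assumption.

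*Case A: a constant share f of each GP's doses goes to minors.* Each GP's total 3-month rate is gamma with shape 1 and mean 3, 6 or 10. The adult rate is (1 − f) × total. There is no true change. Ranges are over the three means.

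| f | Category differs, all-age against adult | Flagged at T6 (6 months): adult / all-age Pb | Flagged at T3 (3 months): adult / all-age Pb |
|---|---|---|---|
| 0% | 0% | 41–47% / same | 17–19% / same |
| 10% | 6–8% | 42–47% / 37–43% | 17–19% / 14–16% |
| 25% | 15–22% | 42–48% / 31–35% | 18–19% / 10–13% |
| 50% | 31–47% | 36–48% / 17–19% | 18–19% / 4–8% |

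Even with an adult baseline, 36–48% of GPs appear to increase at T6 when nothing has changed, because six months are set against three. Correcting age alone at T6 would therefore raise the share of false increases. Both mismatches need correcting together.

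*Case B: doses to minors independent of adult doses.* The adult rate is gamma with shape 1 and mean 3 per 3 months. The mean for minors is 3f/(1 − f), which is 0.75, 2 and 3 for f = 20%, 40% and 50%.

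- Category differs: 18%, 36%, 46% of GPs.
- True 30% rise in adult doses, equal 3-month windows: GPs moving up a category fall from 27% to 20%, 14%, 11%.
- No true change, T6 against Pb: 45% flagged with an adult baseline; 36%, 28%, 23% with an all-age one.

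**Prognostic value.** This is the share of variance in the 6-month adult first-dose count explained by the baseline category, taking half of adult doses as first doses. It is 0.48 with an adult baseline. With an all-age baseline in case B it is 0.43, 0.31, 0.23. If doses to minors are instead proportional to the GP's adult rate, it is about 0.50 to 0.51, which is no loss.

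**Subgroup label.** In case B, 2%, 23%, 40% of GPs in *Regularly* gave five or fewer adult doses in Pb. The label becomes unclear only when the share of minors is high.

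**The case against.** The strongest reply is that section 3.3.1 is silent on age rather than inclusive of minors. It refers to the vaccinations reported later, and those reports are adults-only. A categorical total can be limited to adults without collecting patient data, so the absence of demographics proves nothing about the question. The form itself is not shown. GPs who vaccinate for schools are excluded, which closes one route for doses to minors. Objective 3 is exploratory under 3.1, and section 7 discloses that the main outcomes moved to absolute uptake.

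Most of this stands. A reader might infer that the baseline count definitely covers all ages. The SAP does not say so; that is the plain reading of an item without a limit, and the form may add one. It remains true that the item as written admits minors and that nothing collected for Pb could remove them.

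A reader might also infer that the strata, the primary model and the subgroup analysis are invalid because they rest on another population. The documents do not support this. A variable that describes practice before the intervention need not share the endpoint's population, and the mismatch does not bias the arm comparison. The baseline count is only one of several candidate covariates. Whether precision is lost depends on how doses to minors and adults correlate, and the two cases above give opposite answers. Nor does the mismatch reach every outcome: knowledge and attitude scores are measured on the GP.

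**Conclusion.** The point holds in a limited form. The baseline item lacks the age limit that governs every vaccination-count outcome, and as written this cannot be repaired from the data collected. The real damage is to secondary objective 3, where the two quantities are compared directly and the age mismatch comes on top of a 6-month count against a 3-month reference. For the other three uses the possible cost is some precision and a less clear subgroup label.

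The size is unknown. It is nil if no Pb doses went to minors or if the form already limits the question to adults, and it grows with the share of minors. The figures above are illustrations that rest on assumed dose rates, an assumed share, the assumed link between doses to minors and adults, and the category rule I chose. The primary comparison of first-dose counts at T6 is not put in doubt by this point.

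**What to change.** In 3.3.1, word the baseline item as *doses administered to patients aged at least 18 years during Pb*, for every vaccine so that HPV is not singled out, and keep the four categories. Use that variable throughout: stratification, covariate, subgroup and objective 3. If the form already carries this limit, say so in 3.3.1.

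For objective 3, also compare windows of equal length, for example the 3-month count at T3 against Pb. T3 is already named in the objective.

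If forms without an age limit have been collected, do not go back to GPs after Ti for the main analyses. By then active-arm GPs know the HPV focus, so recall may differ by arm. Instead, label the variable *all-age baseline count* wherever it is used, and do not interpret objective 3 as a measure of change.

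The cost is a few words in the form and the SAP, and a slightly harder recall task for GPs. In the fallback, the cost is the loss of objective 3 as a change measure.

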3.3.2 Outcome Measurements

GPs will document all vaccines administered to patients aged at least 18 years starting on T0 and ending on T12. We will provide enrolled GPs with separate standardized case report forms (CRFs) to report all vaccinations administered during the study period and the follow-up period, respectively. GPs will report the following vaccinations: HPV, MMR, meningococci, pneumococci, TBE, chickenpox, shingles, and hepatitis A/B (combination and individual vaccines). The GPs will send CRFs to the Institute of Primary Care every two months by mail. For the study period and the follow-up period, GPs will report age and sex of patients to whom these vaccines are administered. In addition, only during the study period, they will report whether vaccinations are administered as first/second/third doses or as booster vaccinations as well as whether they are administered upon request by the patient or as recommended by the GP. During the follow-up period, they will only indicate whether vaccinations are administered as first or later doses (without further specification).

3.3.3 Questionnaires

We will assess knowledge about HPV and HPVv and attitudes towards HPVv with a questionnaire administered at Ti (right before the educational session) and at T6. In order to preserve blinding of the control group with respect to HPVv, the survey will be the same for all participants and will include analogous questions about other vaccinations (herpes zoster, pneumococci, and TBE).

The HPVv-specific section of the questionnaire will comprise

- Nine questions on attitudes towards HPVv (4.1–4.9). Of these, 7 questions (4.1–4.3, 4.5–4.8) are Likert-type (levels Disagree/Rather disagree/Neutral/Rather agree/Agree), one is multiple-choice (4.4), and one is single-choice (4.9). Both the single- and multiple-choice question have a free-text option. The sections specific to all other vaccinations will contain the same questions.
- Five single-choice questions on knowledge about HPV (4.10–4.14). Of these, two questions (4.11, 4.12) consist of 7 sub-questions with respectively identical answer options each.

1	TI (/T7 111			T .•	TRA		TT (T 14	
	for eligibility and delivery of the inte	rvention.							
	Table 1. Overview of study timings	. The inclusio	on perio	d refers to	the time fra	ame betweer	1 approach	ing the GP	

Event/Variable	Inclusion period	Ti	T0	Т3	T6	T12
Eligibility determination						
Recruitment						
Randomization						
Baseline characteristics of GPs						
Baseline HPVv count						
Questionnaires						
Delivery of intervention						
Start of HPVv documentation						
Reporting of HPVv documentation						
End of HPVv documentation						

4 Analysis

4.1 Objective Definitions

4.1.1 Primary Objectives

(1) To compare the first-dose HPVv counts at T6 between the intervention group and the control group.

4.1.2 Secondary Objectives

- (1) To compare the first-dose HPVv counts at T3 and T12 between the intervention group and the control group.
- (2) To compare the number of overall HPVv counts at T3, T6, and T12 between the intervention group and the control group.
- (3) To compare the change of overall HPVv counts at T3, T6 and T12 with respect to Pb between the intervention group and the control group.
- (4) To compare the change in HPV-related knowledge at T6 with respect to Ti (before delivery of the intervention) between the active intervention group and the control group.
- (5) To compare the change in attitudes towards HPVv at T6 with respect to Ti (before delivery of the intervention) between the active intervention group and the control group.
- (6) To describe demographic characteristics of patients obtaining HPVv (gender and age).
- (7) To describe the following characteristics of administered HPVv: first dose or later vaccination, request of patient or recommendation by GP (or both), and HPVv administered alone or in combination with other vaccines.

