4.2 Analysis Methods

4.2.1 Descriptive and Baseline Analyses

For all descriptive analyses, we will report counts and percentages for categorical variables and extreme values (minimum and maximum), means and standard deviations, and medians and upper/lower quartiles for continuous variables.

We will provide descriptive summaries for demographic characteristics of participating GPs (age, gender, years of experience in practice, type of practice, type of employment, and workload) and for characteristics of patients who will be administered HPVv (age and gender).

To assess differences in baseline characteristics of GPs in the ITT population among the study arms, we will use Pearson's chi-squared and Fisher's exact tests for categorical variables and Student's *t*-tests and Wilcoxon rank-sum tests for continuous variables as appropriate. The same tests will be performed to assess differences between GPs of the ITT population and GPs lost to follow-up.

We will assess differences of HPVv counts during the study period between the study arms using Pearson's chi-squared and Fisher's exact tests. Cochran Armitage trend test will be used for comparison of HPVv counts between the study arms using the measurement time point as an ordinal variable (with levels T3, T6, T12).

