4.2.4 Analysis of the Secondary Objectives

For the secondary objectives, we will use the following procedures:

- (1) Analogous models as for the primary objective, using the first HPVv dose count at the respective time point and assessing the coefficient estimate of the study arm together with 95% confidence intervals.
- (2) Analogous models as for the primary objective, but using the count of all administered HPVv doses instead of the number of first HPVv doses at the respective time points as the outcome variable. We will base assessment of this objective on the estimated coefficient of the study arm for the respective time points together with 95% confidence intervals.
- (3) We will model this objective with logistic regression. The binary outcome variable will indicate whether the overall count of administered HPVv doses at T6 will have increased with respect to the value indicated for Pb. Model covariates will include GP gender, workload (categorized as for the primary objective), and participation status in the cantonal HPVv program at inclusion.
- (4) To assess this objective, we will use logistic regression on a binary outcome indicating, for each GP, whether their HPV knowledge score will have increased from Ti to T6. The model will include the following covariates: study arm, baseline HPV knowledge score, GP gender, GP workload (categorized as for the primary objective), and participation status in the cantonal HPVv program at inclusion.
- (5) We will assess this objective by a logistic regression model analogous to the model for secondary objective 4. The binary outcome variable will indicate, for each GP, whether their HPVv attitude score will have increased from Ti to T6. Adjustment will occur for the baseline HPVv attitude score instead of the HPV knowledge score.
- (6) Tabulation and assessment of group differences as described in section 4.2.1.
- (7) Tabulation and assessment of group differences as described in section 4.2.1.

For each of the fitted regression models, we will report the results and inferred implications of standard model diagnostics procedures, such as assessment for overdispersion, residual and random effect analyses, influential point analyses, and checks for multicollinearity. Accordingly, we will adapt models as necessary (e.g., by log-transforming continuous variables, by excluding ill-defined variables from the model equations or by considering non-parametric alternatives where deemed appropriate).

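### Secondary objective 6 is about patients, but the data described are administered doses, and the SAP gives no rule for getting from one to the other

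*SAP*

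**What the plan says.** The unit of the objective is the patient. Section 4.1.2, objective 6, reads "To describe demographic characteristics of patients obtaining HPVv (gender and age"), and section 4.2.1 promises descriptive summaries "for characteristics of patients who will be administered HPVv (age and gender").

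The unit of collection is the administered vaccine. Section 3.3.2 has GPs document every listed vaccine given to adults from T0 to T12, and "GPs will report age and sex of patients to whom these vaccines are administered". In the study period (T0 to T6) "they will report whether vaccinations are administered as first/second/third doses or as booster vaccinations". In the follow-up period (T6 to T12) they mark only first or later dose.

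The objective also carries a comparison. Section 4.2.4, item (6), specifies "Tabulation and assessment of group differences as described in section 4.2.1". For categorical GP baseline characteristics, section 4.2.1 says "we will use Pearson's chi-squared and Fisher's exact tests for categorical variables", with t-tests and rank-sum tests for continuous ones. Section 3.1 adds that "A level of significance of 0.05 will be used throughout the analyses".

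**The concern.** One person can receive several HPV doses within the twelve months of documentation. If each dose is a separate record and the records are tabulated as they stand, a recipient of three doses enters the age and gender table three times and a recipient of one dose enters once. Two things follow.

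- The table describes doses, not the people vaccinated. If some age or sex groups receive more doses per person in the window, those groups are over-represented.
- Chi-squared, Fisher, t and rank-sum tests assume independent records. Sex is identical, and age nearly so, across one person's doses. Repeats therefore add apparent sample size without adding information, and the test rejects too often.

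The arms may also differ in their mix of first and later doses. A contrast between arms in recipients' age or sex could then partly reflect that mix. What is at stake is the description of who was reached, and any p-value attached to it.

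**Working it through.** **Inputs from the SAP.** Level 0.05 (section 3.1); two-sided, taken from the statement "we will report two-sided 95% confidence intervals of coefficient estimates" in the same section; dose order first/second/third/booster in the study period and first/later in the follow-up period (section 3.3.2).

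**Inputs not in the SAP, hence assumed.** The shares of patients with one, two and three recorded doses; 100 patients per arm and 40% men where an exact calculation needs them.

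**Formula.** Let m be the number of records per patient, with the same sex and age in each. Compared with what an independent-record test assumes, the variance of an arm contrast is inflated by D = E[m²]/E[m]. The actual two-sided error of a nominal 5% test is 2 × (1 − Φ(1.96/√D)).

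**The nominal figure first.** One record per patient gives D = 1 and an error of 0.050. Simulation of 4,000 null trials gave 0.054 (chi-squared), 0.050 (t) and 0.047 (rank-sum).

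**With repeat doses:**

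| Shares with 1/2/3 doses | E[m] | E[m²] | D | Type I error |
|---|---|---|---|---|
| 90/8/2% | 1.12 | 1.40 | 1.25 | 0.080 |
| 80/15/5% | 1.25 | 1.85 | 1.48 | 0.107 |
| 70/20/10% | 1.40 | 2.40 | 1.71 | 0.134 |
| 50/30/20% | 1.70 | 3.50 | 2.06 | 0.172 |
| 20/40/40% | 2.20 | 5.40 | 2.45 | 0.211 |
| all three doses | 3.00 | 9.00 | 3.00 | 0.258 |

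Worked line for 70/20/10%: E[m] = 0.7 + 0.4 + 0.3 = 1.4; E[m²] = 0.7 + 0.8 + 0.9 = 2.4; D = 2.4/1.4 = 1.714; 1.96/√1.714 = 1.497; error 0.134.

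Simulation gave 0.169 to 0.182 for the 50/30/20% mix and 0.202 to 0.212 for the 20/40/40% mix, across the three tests. For three records per patient, an exact binomial calculation (uncorrected chi-squared, 100 per arm, 40% men) gives 0.279. The gap from 0.258 comes from the discreteness of the counts.

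If m never exceeds 3, then m² ≤ 3m and D cannot exceed 3. The last row is therefore a bound. It would need every recipient, including those who start shortly before T12, to have three recorded doses.

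**Bias in the sex split.** Suppose 40% of patients are men. With 1.5 doses per man and 2.5 per woman, the dose-level share of men is 0.4 × 1.5/(0.4 × 1.5 + 0.6 × 2.5) = 0.6/2.1 = 29%. With equal doses per patient it stays at 40%. The bias therefore depends wholly on an assumed difference that the SAP does not give.

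**After restriction to first doses.** Each patient has at most one record, so D from repetition returns to 1. Clustering remains, because patients are nested in GPs and practices are randomised (section 2.2). With k first-dose patients per GP, D = 1 + (k − 1) × ICC. Assuming k = 5 and ICC = 0.01, D = 1.04 and the error is 0.055. Assuming k = 10 and ICC = 0.10, D = 1.90 and the error is 0.155.

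**The case against.** **The record layout is inferred.** The case report form is not shown, and section 4.3 labels part of its content as patient-level data. This stands as a limit: a reader might infer that the SAP definitely counts patients two or three times, and the text does not establish that. The label in section 4.3 does not establish linkage across visits either. Whichever layout exists, the unit of analysis is left unstated.

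**The tests are not named for patient variables.** Section 4.2.1 promises only summaries for patients' age and gender; it assigns its tests to GP characteristics, loss to follow-up and HPVv counts. This is correct. The tests reach patient variables only through the cross-reference in section 4.2.4. That cross-reference does call for an assessment of group differences, however, and offers no other method.

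**The size is assumed.** A reader might take error rates of 18-28% as the expected result. The SAP gives no dose mix, and milder mixes give about 8-13%. Only the direction is firm, and only if some patients have more than one dose in the window.

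**The consequence is small.** Section 3.1 makes the secondary outcomes exploratory and promises caution with their p-values. This stands, and it sets the weight of the point.

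**Conclusion.** The point holds as a minor one. Objective 6 and section 4.2.1 speak of patients, section 3.3.2 collects doses, and nothing in the SAP connects the two. The SAP does restrict to first doses for the primary objective and for secondary objective 1, so the absence of a rule here leaves dose records as the most natural input.

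Unless the case report form links doses of one person, the type I error of an independent-record comparison lies between just above 5% and about 26-28%, depending on a dose mix that is assumed throughout. These figures cover repetition only and exclude clustering. The age and sex distribution is distorted only to the extent that doses per patient vary with age or sex. A reader might infer that the reported split must be wrong, but the SAP gives no figures that would show this. The primary outcome counts first doses and is not touched.

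**What to change.** In section 4.1.2 (objective 6), section 4.2.1 and section 4.2.4 (item 6), state the unit and base the patient age and gender tables on HPV first-dose records. The planned forms identify first doses in both the study and the follow-up period, and each patient contributes at most one. Show later doses in a separate table, labelled as doses and without tests.

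For the arm comparison, either keep it descriptive or name a method that accounts for clustering by GP and practice. Restricting to first doses while keeping the section 4.2.1 tests would remove the repetition but not the clustering.

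The cost is a few sentences in the SAP and one filter in the code, with no new data; a clustered comparison, if wanted, needs one further model. The downside is that patients who began their series before T0 appear only in the dose table, and the SAP should say so.
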